#### Table 4:Variables (Continued)

Confidential and Proprietary

Classification	Category	Variable	Description
	Effectiveness	Best Overall Response 1: Biochemical Assessment	Assessment of response based on biochemical assessment
		Best Overall Response 2: Bone Marrow Assessment	Assessment of response based on bone marrow assessment
		Relapse and Progression 1	Outcome of relapse or progression detected by bone marrow and/or biochemical/radiologic assessment
Outcome		Relapse and Progression 2: Therapy	Therapy given for treatment of relapse or progression
		Progression Status	Status of progression
		Relapse Status	Status of relapse
		Cause of Death	Primary cause of death and contributing causes of death #1 to #4
		Survival Status	Survival status at last contact

AC = apheresis center, AE = adverse event, ASTCT = American Society for Transplantation and Cellular Therapy, B2M = beta 2 microglobulin, CAR T = chimeric antigen receptor T cell, CRS = cytokine release syndrome, CT = cell therapy, Cytogen. = cytogenetic, d = day, DB = database, ECOG = Eastern Cooperative Oncology Group, FISH = fluorescence in situ hybridization, FU = follow-up, GVHD = graft-versus-host disease, HCT = hematopoietic cell transplantations, ID = Identifier, Intraven. = intravenous, LD = lymphodepleting, MFS = manufacturing site, NT = neurotoxicity, OOS = out of specification, RC = reporting center, SC = site of care, SM = secondary malignancies, TLS = tumor lysis syndrome.

## 9.4. Data Sources and Data Management

Data will be extracted from the EBMT and the CIBMTR electronic cellular therapy forms, which are captured with web-based software used by the 2 registry holders.

The databases and software used by EBMT during the course of the study meet the internationally recognized ethical and scientific quality requirements for designing, conducting, recording and reporting studies involving human subjects. Sites need to be registered to the EBMT Registry system. This registration generates a unique EBMT Center Identification Code (CIC) and includes trainings on the data collection system. Sites initiate patient reporting through the generation of an EBMT Registry Unique Identification Code, which is unique to every patient. In addition, sites may enter an internal Unique Patient Number (UPN). The Therapy Indication Form will identify that the patient is a recipient of ide-cel and triggers a series of forms appropriate for the specific indication that will be under that UPN.

FormsNET3 (FN3), the CIBMTR's web-based data collection system, is compliant with the United States (US) database security requirements established by the Health Resources and Services Administration Office of Information Technology and with the Food and Drug Administration (FDA) 21 Code of Federal Regulations (CFR) Part 11. Sites need to be registered as a CIBMTR member and sign a Master Healthcare Data Agreement (MHA) and a Sample Submission Agreement to allow the transfer of data between organizations (CIBMTR and Site). Upon MHA completion, site staff are provided access to FN3, and are provided trainings on the CIBMTR data collection processes including the use of the FN3 system. Sites initiate patient reporting through the FN3 generation of a CIBMTR Research Identification (CRID) number, which is unique to every patient. The Therapy Indication Form will identify that the patient is a recipient of ide-cel and triggers a series of forms appropriate for the indication. With the CRID, the patient's record can be tracked over time as well as multiple indications. In addition, data are managed through a role-based security model and the CIBMTR data collection, data storage and data sharing systems are externally audited every year.

Data from the two registries will be exported following internationally agreed data standards for clinical data sharing (eg, Study Data Tabulation Model [SDTM]-Clinical Data Interchange Standards Consortium [CDISC]) and then combined into Analysis Data Model (ADAM)-like data sets including derived variables to allow consistent and periodic analyses. These data sets will include the characteristics, outcome variables and other covariates. Data dictionaries will be prepared to describe all variables and values included. If in the future, analyses software specifications change, formats and file conventions will be modified and adapted to the required needs.

The data from all sources will be integrated into one internal data system built and managed by the Sponsor.

For details on data monitoring and source data verification refer to Section 9.7, further below.

## 9.5. Study Size

Since this is a single-arm noninterventional cohort study with no comparisons, no statistical hypothesis testing and no formal powered sample size calculation is possible. Instead, a fixed number of 1000 patients from registries is used based on pragmatic non statistical reasons, which is considered feasible within the estimated 5-year selection period. The study size is justified by providing precision estimates (see below).

For the chosen sample size of 1000 patients, in general there would be a 95% chance to observe at least one event if the true incidence is  $\geq 0.3$  events per year (using normal approximation according to Wald).

To justify the sample size, precision estimates for example incidences, taken from the literature, are provided by calculating exact 95% Clopper Pearson confidence intervals (based on a binomial distribution). (see table below).

Assumed incidences for secondary malignancies were based on SPMs data from Mahindra and co-workers (Mahindra, 2015) and Costa and co-workers (Costa, 2018). The incidences for CRS and neurotoxicity correspond to incidences reported as AEs of special interest (AESIs) by Raje and co-workers (Raje, 2019) based on the CRB-401 trial (ClinicalTrials.Gov#: NCT02658929). The populations from these three sources are characterized as follows:

- **Mahindra et al population**: MM patients with an age range from 22 to 80 years and a first autologous stem cell transplantation (auto SCT) within 18 months of MM diagnosis, reported to the CIBMTR between 1990 and 2010.
- **Costa et al population**: Three cohorts of patients with an age range from 19 to 64 years, with MM as first malignant neoplasm, reported to the SEER between 1995 and 2009.
- **Raje et al population**: MM patients in the US with an age range from 37 to 75 years and an Eastern Cooperative Oncology Group (ECOG) score of 0 or 1.

Data Source	Description	Observed I		Incidence	Clopp Pea	ars 95% CI
		Patients	Incidence	Proportion	lower	upper
					(for 1000 j	patients)
(Mahindra, 2015)	overall SPMs (1990-2010)	4161	145	0.035	0.025	0.048
	excluding NMSC, including MDS					
(Costa, 2018)	overall SPMs (1995-2009)	9833	420	0.043	0.031	0.058
	excluding NMSC, excluding MDS					
(Raje, 2019)	$CRS \ge Grade 3$	33	2	0.061	0.047	0.078
(Raje, 2019)	Neurotoxicity $\geq$ Grade 3	33	1	0.030	0.020	0.043

Table 5:	Assumed	Incidence	for S	Safety	Endpoints
----------	---------	-----------	-------	--------	-----------

CI = confidence interval; Clopp Pears = Clopper Pearson; CRS = cytokine release syndrome;

MDS = myelodysplastic syndrome; NMSC = nonmelanoma skin cancer; SPM = second primary malignancy.

Thus, in conclusion, if similar incidences are observed in this study, this would provide sufficient precision for a meaningful interpretation of the observed incidences.

## 9.6. Data Analysis

In this noninterventional cohort study, results will be analyzed and reported descriptively; no formal hypothesis testing is carried out.

Confidence intervals will be presented as 2-sided 95% intervals unless specified differently for specific analyses.

Summary statistics will consist of the number and percentage of patients in each category for discrete variables, whereas for continuous variables the sample size, mean, median, standard deviation, minimum, and maximum will be given.

A detailed statistical analysis plan (SAP) will be finalized before the first analysis.

#### 9.6.1. Analysis Populations

Due to the observational nature of the study, no formal analysis populations such as intent to treat or a per protocol population can be defined. Instead, the term "analysis sets" will be used.

• Infused Set (IS): Is defined as all patients selected from the registry and meeting the eligibility criterion (see Section 9.2.1), where baseline and disease classification information is available.

• Safety and Effectiveness Set (SES): Is defined as all patients from the IS with information collected at least after 100 days.

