## 9. **RESEARCH METHODS**

## 9.1. Study Design

This study is designed as a non-interventional cohort study that is part of multiple registries of patients with MM treated with ide-cel in the postmarketing setting which includes patients treated with out of specification (OOS) product.

Data from a total of 1000 patients treated with ide-cel, including a minimum of 300 EU patients, will be collected until death, lost to follow-up, or withdrawal of consent, or up to 15 years, whichever occurs first. This registry study is expected to require up to 5 years to select the planned 1000 patients.

No comparison groups will be defined and no inferential testing will be performed.

Secondary malignancies must be reported to the Sponsor by the treating physicians in order to expedite AE reporting. In the event that a secondary malignancy of T cell origin is suspected, the Sponsor should be contacted to obtain instructions on the collection and transfer of a tumor tissue sample for testing in a separate process, outside of this PASS. In the postmarketing setting, the Sponsor will offer transgene assay service testing for all secondary malignancies of suspected T cell origin where a sample is available, as a routine pharmacovigilance measure to ensure gathering the most information possible for clinical assessment of the reported spontaneous case.

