#### 9.2.1. Eligibility Criteria

All patients who meet the following eligibility criterion will be selected from the registries:

• Patient must have been treated with at least one infusion of ide-cel in the postmarketing setting. Patients treated with OOS product will also be eligible.

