#### 9.6.3. Baseline and Demographic Characteristics

Patients are included into the registry from 2 weeks prior to the ide-cel infusion to any time afterwards. Baseline data are retrospectively reported by data managers after the administration of ide-cel and are collected only once. All information, including any medical history and measurements done prior to the administration of ide-cel, becomes available in the registry as baseline data.

The baseline data will be summarized using descriptive statistics. Individual patient listings will also be provided to support the summary tables. The number and percentage of patients in each of the categories, as listed in Section 9.3, will also be given.

The following baseline data will be presented:

- **Demographics:** Demographic information collected at baseline will be presented using descriptive statistics.
- **Disease History/Comorbidities**: The frequency of patients with at least one comorbidity, as well as frequency counts of different comorbidities will be presented. The ECOG Performance Status score and disease status at infusion will be summarized by frequency counts.
- **Prior Therapy/Prior Medications**: Number of lines of prior therapies will be presented using descriptive statistics. Number of lines of prior therapies will be described as frequency counts. A frequency tabulation of the number of patients with the different types of prior therapies will be given. Also, a frequency tabulation of whether the patient had prior hematopoietic cell transplantations (HCTs) and the types of prior HCTs will be given.
- Lymphodepleting Treatment: A frequency tabulation of the list of lymphodepleting agents will be given.

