## 9.8. Limitations of the Research Methods

As this is an observational PASS based upon secondary use of data, sporadic missing data are inevitable, because certain variables may not have been routinely recorded in the patient medical charts. Furthermore, data will also be missing due to gaps in the follow-up (as routine scheduled visits cannot be mandated in an observational study), and loss to follow-up, especially in this study with a planned duration of 15 years. Details of how missing data are handled are also outlined in the SAP.

The above-mentioned potential issue can lead to significant biasing effects on time to event analyses as well as analyses quantifying a duration. In the EBMT and the CIBMTR registries, data are recorded at baseline, 100 days, 6 months and then yearly. Thus, owing to center specific different levels of compliance, a high variability in the recording of assessment dates is to be expected.

To minimize selection bias, sites are requested to ask every patient treated with ide-cel to share data with the registry. Nevertheless, not all patients will consent to have their data sent to the

Confidential and Proprietary

EBMT or the CIBMTR registries, possibly resulting in a biased sample of patients. A high rate of attrition (particularly if mortality is not captured well) could bias the results. In addition, in order to monitor the reporting, the study team will reconcile shipped products to each center participating in the study with the subsequent compliance of the patient and center with the study.

Additionally, as with every observational study, there will be unmeasured factors that can confound safety and effectiveness analyses. This PASS will attempt to collect accurate and complete data on all known critical confounders; however, residual confounding is always a possibility in any observational study analysis.

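### The Infused Set leaves out treated, eligible patients whose baseline or disease classification data are missing, so every safety and survival estimate carries a filter that can depend on events after infusion

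*Protocol*

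**What the plan says.** Section 9.2.1 has one eligibility criterion: "Patient must have been treated with at least one infusion of ide-cel in the postmarketing setting". It asks for no baseline data.

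Section 9.6.1, repeated in the Abstract, defines the Infused Set (IS) as eligible registry patients "where baseline and disease classification information is available". The Safety and Effectiveness Set (SES) "Is defined as all patients from the IS with information collected at least after 100 days". No third set is defined.

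On timing, section 9.6.3 states: "Baseline data are retrospectively reported by data managers after the administration of ide-cel and are collected only once". Section 9.8 expects gaps: "sporadic missing data are inevitable, because certain variables may not have been routinely recorded in the patient medical charts". The same section expects compliance to differ between centres.

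On size, section 9.1 plans "Data from a total of 1000 patients treated with ide-cel, including a minimum of 300 EU patients", and Table 5 in section 9.5 gives precision for 1000 patients. The Protocol does not say whether the 1000 are counted before or after the IS condition is applied. It does not list the variables that must be present, and it gives no expected rate of missing baseline data. Sections 9.6.5.1 and 9.6.5.2 do not name the set used for the safety percentages.

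**The concern.** A set named for infusion should hold every infused, eligible patient. This one also needs information that is entered after treatment. A patient who dies early, moves to another hospital or is treated at a centre with poor reporting may be more likely to lack it, and would then leave the denominator, and the numerator if an event occurred.

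The filter has no stated analytic use. The primary outputs are incidence proportions, incidence rates and cumulative incidence, and none is described as adjusted for baseline covariates. OS and PFS need the infusion date but no other baseline item.

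Section 9.6.5.2 says that secondary malignancies, pregnancies and deaths are reported on event-driven forms. Such an event can therefore be in the registry for a patient who is outside the IS. Secondary malignancy is the first primary endpoint listed. In a study whose main product is a set of incidences, a filter of this kind could understate risk. It also works against section 9.8, where sites are asked to approach every treated patient in order to limit selection bias.

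**Working it through.** **1. The definitions side by side**
- Eligible (9.2.1): at least one postmarketing infusion.
- IS (9.6.1): eligible, and baseline and disease classification information available.
- SES (9.6.1): in the IS, and information collected after at least 100 days.

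Since SES ⊂ IS ⊂ eligible, the availability condition applies whichever of the two sets is used.

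**2. Reproducing Table 5**

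The exact 95% limits are the Beta quantiles B(0.025; x, n − x + 1) and B(0.975; x + 1, n − x), with n = 1000.

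| Endpoint | x | Computed | Table 5 |
|---|---|---|---|
| SPM, transplant registry source | 35 | 0.0245–0.0483 | 0.025–0.048 |
| SPM, population cancer registry source | 43 | 0.0313–0.0575 | 0.031–0.058 |
| CRS Grade ≥ 3 | 61 | 0.0470–0.0777 | 0.047–0.078 |
| Neurotoxicity Grade ≥ 3 | 30 | 0.0203–0.0426 | 0.020–0.043 |

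All limits agree to within 0.001. The stated precision therefore takes all 1000 patients as the denominator.

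**3. Precision if patients are lost**

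The exclusion rates are assumptions. CRS Grade ≥ 3, x = 2/33 of n, rounded:

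| n | x | 95% CI | Width |
|---|---|---|---|
| 1000 | 61 | 0.0470–0.0777 | 0.0307 |
| 950 | 58 | 0.0467–0.0782 | 0.0315 |
| 900 | 55 | 0.0464–0.0788 | 0.0324 |
| 800 | 48 | 0.0446–0.0788 | 0.0342 |
| 700 | 42 | 0.0436–0.0802 | 0.0367 |

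At n = 900 the ratio of widths is 0.0324/0.0307 = 1.055, in line with √(1000/900) = 1.054.

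**4. Bias if exclusion is related to the event**

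Let p = 0.061 be the true incidence (Table 5), m the fraction excluded, and r the ratio of the exclusion probability in patients with the event to that in patients without it. Both m and r are assumptions.
- Exclusion probability without the event: q = m / (p·r + 1 − p).
- Reported incidence: p(1 − r·q) / (1 − m).

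For m = 0.10:
- r = 1: q = 0.10, and the reported value is 0.061 × 0.90/0.90 = 6.1%.
- r = 2: q = 0.10/1.061 = 0.0943, and the reported value is 0.061 × (1 − 0.1885)/0.90 = 5.5%.
- r = 3: q = 0.10/1.122 = 0.0891, and the reported value is 0.061 × (1 − 0.2674)/0.90 = 5.0%.

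| Excluded | r = 1 | r = 2 | r = 3 |
|---|---|---|---|
| 2% | 6.1% | 6.0% | 5.9% |
| 5% | 6.1% | 5.8% | 5.6% |
| 10% | 6.1% | 5.5% | 5.0% |
| 20% | 6.1% | 4.75% | 3.55% |

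A ratio below 1 would move the estimate upwards. The documents do not settle the direction.

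**The case against.** The strongest reply is that 'available' need not mean 'complete'. Table 4 counts the patient identifier, infusion date and primary disease as baseline items, so a patient with no baseline information at all could not be recognised as infused or given a time origin. On that reading the clause asks for little more than identification, and the SAP may say so. The missing data described in section 9.8 are sporadic gaps in single variables, not absent baseline records. Disease classification is also the only condition in the set definitions that concerns the disease, since the eligibility criterion does not mention multiple myeloma.

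Some of this stands. The time origin and the indication must be kept in any new definition. The SAP could narrow the clause, and section 9.6.2 would make the number selected and the disposition visible. Shipped products are also to be reconciled by centre. None of this removes a stated rule that selects patients on data entered after treatment. Section 9.4 already identifies the ide-cel recipient and the indication through the Therapy Indication Form, so the clause is not needed for either purpose.

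Three stronger readings are not supported:
- A reader might infer that the denominator does fall below 1000 and that the Table 5 precision is lost. No exclusion rate is given, the stage at which the 1000 are counted is not stated, and the loss of precision in step 3 is small.
- A reader might take the IS to be the safety denominator. The safety sections assign no set, and the set named for safety is the SES.
- A reader might say that a patient with early fatal CRS is lost only because of a baseline form. The 100-day condition of the SES could remove that patient even with complete baseline data.

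**Conclusion.** The point holds as a selection problem written into the set definitions. The IS drops eligible, infused patients on the availability of data reported after infusion, the SES inherits this, and the Protocol defines no set without the filter.

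The size is not known. Under the assumption of 10% excluded and a true Grade 3 or higher CRS incidence of 6.1%, the reported value runs from 6.1% (exclusion unrelated to the event) to 5.0% (event patients three times as likely to be excluded). At 2% excluded it stays between 6.1% and 5.9%. Whether the denominator falls short of 1000 depends on when the 1000 are counted. Possible bias is the reason to change the definition; the wider interval is a minor matter.

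**What to change.** In section 9.6.1 and in the Abstract:
- Define the IS as all registry patients with at least one recorded postmarketing ide-cel infusion, with a known infusion date, for multiple myeloma as identified by the Therapy Indication Form.
- Delete the condition on availability of baseline and disease classification information.

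In section 9.6.3, show absent baseline items as a 'missing' category in the baseline tables. In section 9.1 or 9.5, state at which stage the 1000 patients are counted. It would also help to name the set used for each safety analysis.

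The cost is a change of wording in a few places. No new data are needed. The change does not resolve the 100-day condition of the SES, which is a separate issue.

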#### **Analysis Populations:**

Due to the observational nature of the study, no formal analysis populations such as intent to treat or a per protocol population can be defined. Instead, the term "analysis sets" will be used.

- **Infused Set (IS):** Is defined as all patients selected from the registry and meeting the above-mentioned eligibility criterion, where baseline and disease classification information is available.
- Safety and Effectiveness Set (SES): Is defined as all patients from the IS with information collected at least after 100 days.

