Administration of cellular products such as CAR-expressing T cells can be associated with cytokine release syndrome (CRS), a systemic inflammatory response caused by the release of various cytokines (Lee, 2019; Gardner, 2017).

Cytokine release syndrome manifests typically with characteristic clinical symptoms such as fever, tachypnea, headache, tachycardia, hypotension, rash, and/or hypoxia. Symptoms and severity of CRS are highly variable, and management can be complicated by concurrent conditions.

Cytokine release syndrome occurs in a variable fraction of patients after CAR T cell therapy, with incidences ranging from 35% to 93%. The variable incidence and severity of CRS between studies is likely due to differences in CAR construct, CAR T cell manufacturing, diagnosis, disease burden, eligibility criteria, and the systems used to grade CRS (Hirayama, 2019).

CAR T cell therapy is associated with unique neurotoxicities. Neurologic symptoms may appear within 4 weeks after CAR T cell infusion and include altered mental status, aphasia, altered level of consciousness, and seizures or seizure-like activity.

Focal neurologic deficits, seizures, encephalopathy, and acute cerebral edema have been reported, but are infrequent (Santomasso, 2018). Rates and severity of neurotoxicities vary, with severe (Grade  $\geq$  3) manifestations observed in 12% to 28% of patients receiving CAR T cell therapy (Schuster, 2019; Abramson 2018; Neelapu, 2017).

Recently, a panel of experts developed the American Society for Transplantation and Cellular Therapy Consensus Grading, a list of recommendations, proposed new definitions and grading for CRS and neurotoxicity to better categorize the severity of these toxicities (Lee, 2019).

Other toxicities that are important to assess in recipients of CAR T cells include prolonged time to recover blood counts and the development of infections (Hirayama, 2019).

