The most frequently reported AEs in the ide-cel-treated population on or after ide-cel infusion (preferred terms [PTs] reported in  $\geq$  40% of subjects) were neutropenia (91.4%), CRS (83.6%), anemia (69.5%), thrombocytopenia (63.3%), and leukopenia (42.2%). The most frequently reported Grade 3 or 4 AEs ( $\geq 20\%$ ) were neutropenia (89.1%), anemia (60.2%), thrombocytopenia (52.3%), leukopenia (39.1%), and lymphopenia (26.6%). The most frequently reported serious adverse events ( $\geq$  5% of subjects) were CRS (17.2%), general physical health deterioration (10.2%), pneumonia (8.6%), and febrile neutropenia (7.0%). The overall frequency of subjects with CRS was 83.6%, with 5.5% of subjects having  $\geq$  Grade 3 CRS and 1 subject having Grade 5 CRS. Neurotoxicity (investigator-identified AE related to ide-cel) was a common AE after ide-cel but was mainly Grade 1 or 2 in severity, with only 3.1% of subjects reporting Grade 3 events and no Grade 4 or 5 events reported. Infection, which is a leading cause of death in patients with myeloma (Nucci, 2009), was reported in 68.8% of subjects after ide-cel infusion, with 21.1% of subjects having Grade 3 or 4 infections and 5 subjects (3.9%) having infections leading to death. There were 8 (6.3%) subjects with reported secondary malignancies after initial ide-cel infusion and an additional 1 subject with reported secondary malignancy after ide-cel retreatment; none of these events were consistent with clonal T cell malignancies.

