#### 9.6.4. Effectiveness Analysis

#### 9.6.4.1. Analysis of the Secondary Effectiveness Endpoints

- **Overall Survival (OS)**: Overall survival is defined as the time from the date of first infusion to the date of death due to any cause. All patients will be followed for survival information, regardless of whether they receive additional treatment post-infusion. Patients who are alive at last contact date will be censored at that time, but no censoring will be done for additional treatment.
- **Progression-Free Survival (PFS)**: PFS is defined as the time from the date of first idecel infusion to the date of event defined as the first documented relapse or progression or death due to any cause, whatever happens first. Patients who are alive at last contact date will be censored at that time, but no censoring will be done for additional treatment.
- **Time To Event (TTE) Analysis:** Kaplan-Meier estimates and the associated 95% CIs of the median, 25th and 75th percentile will be presented. The two-sided 95% CIs will be computed using the log-log transformation. The survivor function will be displayed graphically using a KM curve.

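### The Safety and Effectiveness Set requires information after Day 100 with no exception for earlier death, so followed literally it would drop early fatal toxicity and early deaths

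*Protocol*

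**What the plan says.** Eligibility (Section 9.2.1) asks only for exposure: "Patient must have been treated with at least one infusion of ide-cel in the postmarketing setting". Section 9.6.1 then defines two sets. The Infused Set is the eligible patients "where baseline and disease classification information is available", with no follow-up condition. The SES is "all patients from the IS with information collected at least after 100 days". The Abstract repeats the same wording, and neither place provides for a patient who dies before Day 100.

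The analyses themselves start at infusion. Section 9.6.4.1 states: "Overall survival is defined as the time from the date of first infusion to the date of death due to any cause". It adds: "All patients will be followed for survival information, regardless of whether they receive additional treatment post-infusion". Patients alive at last contact are censored at that date. Section 9.6.5.1 makes the primary endpoint the incidence and severity of selected adverse events reported after infusion. Section 9.6.5.2 includes Grade 5 organ toxicities in the summaries. None of these sections says which set it uses.

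On data flow, Section 9.8 gives the recording times as baseline, 100 days, 6 months and then yearly. Section 9.6.5.2 says that most toxicities are reported in aggregate for the preceding period, while deaths arrive on a separate event-driven form.

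**The concern.** Membership of the SES depends on something that happens after infusion, whereas the endpoints count from infusion. The toxicities of most interest fall inside the first 100 days. Section 7.2.2 says: "Neurologic symptoms may appear within 4 weeks after CAR T cell infusion". Fatal toxicity has been seen with this product: Section 7.2.3 reports "1 subject having Grade 5 CRS" in Study MM-001, and five subjects with infections leading to death.

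If the SES is the denominator, a patient who dies of an early toxicity disappears from both sides of the fraction, and the severity distribution loses its worst cases first. OS begins with a 100-day stretch in which no death can be recorded. A patient alive but lost before Day 100 is deleted, along with any toxicity already recorded, instead of being censored at last contact as Section 9.6.4.1 provides. For a safety study whose primary output is incidence and severity, removing early deaths can only make OS look better, and it lowers toxicity rates wherever the toxicity is over-represented among those deaths.

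**Working it through.** **Inputs from the protocol.** Planned n = 1000 and assumed Grade ≥3 CRS proportion 0.061 (Section 9.5, Table 5). For MM-001 (Section 7.2.3): 128 treated, 5.5% with Grade ≥3 CRS (0.055 × 128 = 7.04, so 7 patients), one Grade 5 CRS, five fatal infections, median PFS 8.6 months.

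**Assumed, because the protocol does not give them.** Share dying before Day 100, q = 1%, 3%, 5% or 10%; true 12-month OS of 70%; 30% of early deaths with Grade ≥3 CRS; exponential PFS.

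**Step 1, the plan's own figure.** The exact Clopper-Pearson interval for 61/1000 is 0.0470 to 0.0777, which matches the printed 0.047 to 0.078. The other three rows of Table 5 also reproduce. That precision presumes that all 1000 patients are in the denominator. Under the literal SES, n = 1000 × (1 − q), before any losses.

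**Step 2, OS.** With deaths before Day 100 removed, the curve after Day 100 reads S(t)/(1 − q), and survival at Day 100 reads 100%.

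**Step 3, Grade ≥3 CRS.** The rate becomes (61 − 0.30 × 1000q) / (1000 − 1000q). More generally it falls whenever Grade ≥3 CRS is more common among early deaths than the overall 6.1%.

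**Step 4, PFS.** A patient who progresses before Day 100 and has later information stays in and counts as an event; only early deaths and losses go. With λ = ln 2/8.6, removing the early deaths gives a median of −ln[0.5(1 − q)]/λ.

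| q (assumed) | SES n | Day-100 survival, true → SES | 12-month OS, true 70% → SES | Grade ≥3 CRS, 6.1% → SES | Median PFS, 8.6 months → SES |
|---|---|---|---|---|---|
| 1% | 990 | 99% → 100% | 0.70/0.99 = 70.7% | 58/990 = 5.9% | 8.7 |
| 3% | 970 | 97% → 100% | 0.70/0.97 = 72.2% | 52/970 = 5.4% | 9.0 |
| 5% | 950 | 95% → 100% | 0.70/0.95 = 73.7% | 46/950 = 4.8% | 9.2 |
| 10% | 900 | 90% → 100% | 0.70/0.90 = 77.8% | 31/900 = 3.4% | 9.9 |

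**Step 5, MM-001 as an example.** If the one fatal CRS fell before Day 100 (timing not given), Grade ≥3 CRS moves from 7/128 = 5.5% to 6/127 = 4.7%, and Grade 5 CRS from 1/128 = 0.8% to zero. If the five fatal infections were also early and none overlapped, 6/128 = 4.7% of treated patients would leave the set.

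**Step 6, the milder reading.** Suppose the phrase means having at least the 100-day report. That report covers days 0 to 100, so an early death with a completed report stays in. But Section 9.6.5.2 routes deaths through their own form, and nothing says that this form qualifies a patient for the SES or that a 100-day report is also completed for someone who has died. Inclusion would then depend on what each center files, and Section 9.8 expects compliance to differ between centers.

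**The case against.** The strongest reply is that the wording need not mean survival past Day 100. Day 100 is the first scheduled report, and the phrase concerns when information is collected, not whether the patient is alive. Baseline data are entered retrospectively (Section 9.6.3), and follow-up on an early death might be too. Other parts of the protocol suggest that early deaths are meant to count: data are collected until death (Section 9.1), disposition includes discontinuation due to death (Section 9.6.2), Grade 5 organ toxicities are summarised, and competing-risk analyses are planned. Assigning endpoints to sets is commonly left to a SAP, which is not available here.

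Much of this stands. It would be too strong to infer that the plan certainly removes early fatal cases: no section ties the safety endpoints or OS and PFS to the SES, and that link rests on the set's name. A reader might also infer that PFS, like OS, is shifted by a full 100 days. It is not. A shift from 8.6 to 11.9 months (8.6 + 100/30.4375) would require early progressions to be removed as well, and the definition does not do that.

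What does not stand is the idea that the other provisions repair the definition. None of them says that an early death belongs in the SES, and the milder reading leaves deaths known only from the event-driven form in doubt. The definition is fixed in the protocol, so a SAP that applied it as written would inherit the problem.

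**Conclusion.** The definition is defective as written. On the literal reading, and if the SES serves the analyses its name implies, deaths and losses before Day 100 leave the safety results, and OS has no deaths in its first 100 days. That conflicts with counting adverse events from infusion (Section 9.6.5.1), summarising Grade 5 organ toxicities (Section 9.6.5.2) and following all patients for survival with censoring at last contact (Section 9.6.4.1). PFS is affected only through early deaths and losses. On the milder reading, exclusion of early deaths is possible but not certain.

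The direction for OS is sure once early deaths are excluded; the size is not. The protocol contains no Day-100 mortality, so the tabulated figures illustrate scale under stated assumptions and do not estimate the bias. The MM-001 example depends on a single death of unstated timing. The point is worth correcting before the first analysis because it bears on the primary safety output.

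**What to change.** In Section 9.6.1 and the Abstract, redefine the SES as all Infused Set patients with any post-infusion information, stating that a death report before Day 100 qualifies. In Section 9.6.5.1, name this set for the primary safety endpoints. In Section 9.6.4.1, state that OS and PFS use all infused patients from first infusion, with the censoring at last contact already described. Say plainly that this is wider than the present Infused Set, which also requires baseline and disease classification data.

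At each data cut, restrict Day-100 incidence denominators to patients infused at least 100 days earlier, regardless of vital status or form receipt. Report the number of infused patients with no post-infusion information. Keep a Day-100 condition only for an analysis labelled as a landmark analysis.

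The cost is a revised definition and a few sentences in the protocol, carried into the SAP. No new data collection is needed, since deaths are already reported on their own form. The downside for the sponsor is that reported toxicity and survival may be less favourable than under the literal SES.
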